- To develop exposure/biomarker/clinical endpoint models (whenever possible, using a mechanism-based approach) for both efficacy and safety data that will allow exploration of alternative dosing regimens with a better efficacy/safety profile than the lenvatinib 18-mg plus everolimus 5-mg dose.

Study Design

Originally, this was a multicenter, randomized, double-blind study conducted as a postmarketing requirement by the US Food and Drug Administration (FDA) and the European Medicines Agency (EMA) to evaluate an alternate dose regimen for lenvatinib in combination with everolimus. As of 14 Jul 2018, all ongoing subjects' treatment assignment has been unblinded to investigational site personnel, and the study will be conducted in an open-label fashion. The investigational site personnel and study subjects will be unblinded as to the treatment assignment for all newly enrolled subjects.

In subjects with advanced renal cell carcinoma (RCC) following one prior anti-angiogenic treatment, the current approved lenvatinib dose is 18 mg daily in combination with everolimus 5 mg daily. This study will evaluate the combination of lenvatinib and everolimus in subjects with advanced predominant clear cell RCC following one prior vascular endothelial growth factor (VEGF)-targeted treatment at 14-mg starting dose of lenvatinib and allow up-titration of lenvatinib to determine whether this regimen provides comparable efficacy but has a better safety profile than the 18-mg starting dose. The 14-mg starting dose will be escalated to 18 mg if no Grade 2 (intolerable) or any \geq Grade 3 treatment-emergent adverse events (TEAEs) that require dose reduction are observed in the first cycle (4 weeks) of treatment. If Grade 2 (intolerable) or Grade 3 or 4 TEAEs are observed, the lenvatinib dose will be reduced, as described below in the dose reduction section. Both lenvatinib and everolimus will be administered orally (PO) and once daily (QD).

Eligible subjects will have measurable disease according to Response Evaluation Criteria in Solid Tumors Version 1.1 (RECIST 1.1) and will be randomly assigned to each treatment arm in a 1:1 ratio. The total sample size will be approximately 338 subjects. Randomization will follow a predefined randomization scheme based on the following stratification factors: Memorial Sloan-Kettering Cancer Center (MSKCC) prognostic groups (favorable, intermediate, or poor risk); and whether subjects have had a prior PD-1/PD-L1 treatment (yes or no).

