9 INVESTIGATIONAL PLAN

9.1 Overall Study Design and Plan

Originally, E7080-G000-218 was designed as a multicenter, randomized, double-blind study, conducted as a postmarketing requirement of the US Food and Drug Administration (FDA) and the European Medicines Agency (EMA) to evaluate an alternate dose regimen for lenvatinib in combination with everolimus. As of 14 Jul 2018, all ongoing subjects' treatment assignment has been unblinded and the study will be conducted in an open-label fashion. The investigational site personnel will be unblinded as to treatment assignment for all newly enrolled subjects. Lenvatinib 18 mg daily in combination with everolimus 5 mg

daily is approved in the US and EU for the treatment of adult patients with advanced RCC following 1 prior VEGF-targeted therapy.

This study will evaluate the combination of lenvatinib and everolimus at a 14-mg starting dose of lenvatinib and allow up-titration of lenvatinib to determine whether this alternate dose regimen provides comparable efficacy but has a better safety profile than the 18-mg starting dose in this subject population. The 14-mg starting dose will be escalated to 18 mg if no Grade 2 (intolerable) or any \geq Grade 3 TEAEs that require dose reduction are observed in the first cycle (4 weeks) of treatment. If Grade 2 (intolerable) or Grade 3 or 4 TEAEs are observed, the lenvatinib dose will be reduced, as described in the dose reduction section ([Section 9.4.2](#)). Both lenvatinib and everolimus will be administered orally (PO) and daily (QD).

Eligible subjects will have measurable disease according to Response Evaluation Criteria in Solid Tumors Version 1.1 (RECIST 1.1) and will be randomly assigned to each treatment arm in a 1:1 ratio. The total sample size will be approximately 338 subjects. Randomization will follow a predefined randomization scheme based on the following stratification factors: Memorial Sloan-Kettering Cancer Center (MSKCC) prognostic groups (favorable, intermediate, or poor risk); and whether subjects have had a prior PD-1/PD-L1 treatment (yes or no).

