For subjects in the 14-mg QD (+everolimus 5 mg) arm, if there are no intolerable Grade 2 or any \geq Grade 3 TEAEs that require dose reduction in the first 28-day cycle (ie, the first 4 weeks of treatment), lenvatinib dose will be escalated to 18 mg QD (+everolimus 5 mg). See the Interactive Voice and Web Response System (IxRS) Manual and revised Pharmacy Manual for further instructions.

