9.4.2 Criteria for Interruption of Treatment, Dose Reduction and Resumption of Treatment

Dose reductions for toxicity may be instituted at any time as necessary.

Adverse events will be graded using Common Terminology Criteria for Adverse Events (CTCAE) version 4.03.

Dose reduction and interruptions for subjects who experience lenvatinib-everolimus combination therapy-related toxicity (except hypertension and non-infectious pneumonitis)

will be managed as described in Table 2, “Dose Modification Guidelines for Lenvatinib-Everolimus Combination Treatment-Related Toxicity.” For treatment-related hypertension and non-infectious pneumonitis, refer to Management of Hypertension (Section 9.4.2.2) and Management of Non-infectious Pneumonitis (Section 9.4.2.5) for dose modification guidelines. Investigators will decide the probability of the event being related to 1 or both drugs as to whether dose modification of 1 or both drugs is required.

Lenvatinib dose reductions will occur in succession based on the previous dose level. The lenvatinib and everolimus dose may not be increased at a later date, unless the dose was mistakenly decreased; in this situation, the sponsor’s approval is required to increase the dose. Subjects in either arm will be allowed a maximum of 3 lenvatinib dose reductions for lenvatinib-related toxicity.

Refer to the subsections below for management of proteinuria (Section 9.4.2.3), diarrhea (Section 9.4.2.4), infections (Section 9.4.2.6), blood glucose/lipids (Section 9.4.2.7), hepatotoxicity (Section 9.4.2.8), thromboembolic events (Section 9.4.2.9), posterior reversible encephalopathy syndrome/reversible posterior leukoencephalopathy syndrome (PRES/RPLS) (Section 9.4.2.10), and hypocalcemia (Section 9.4.2.11), as appropriate, in addition to consulting the dose modification table (Table 2).

Table 2 Dose Modification Guidelines for Lenvatinib-Everolimus Combination Treatment-Related Toxicity

Treatment-Related Toxicity ^{a,b}	Management	Dose Adjustment
Grade 1 or Tolerable Grade 2		
	Continue treatment	No change
Intolerable Grade 2^{c,d,e} or Grade 3^f		
First occurrence	Interrupt lenvatinib and everolimus until resolved to Grade 0 - 1 or tolerable Grade 2	Reduce lenvatinib dose 1 level and resume everolimus at the same dose as prior to dose interruption ^b

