Second occurrence (same toxicity or new toxicity)	Interrupt lenvatinib and everolimus until resolved to Grade 0 – 1 or tolerable Grade 2	Reduce lenvatinib dose 1 level. Dose reduction of everolimus to 5 mg every other day may be considered for Grade 3 toxicity ^e
Third occurrence (same toxicity or new toxicity)	Interrupt lenvatinib and everolimus until resolved to Grade 0 - 1 or tolerable Grade 2	Reduce lenvatinib dose 1 level. Dose reduction of everolimus for Grade 3 toxicity may be considered as follows: ^e i) if 5 mg daily everolimus at event onset, reduce to 5 mg every other day or ii) if 5 mg every other day everolimus at event onset, discontinue

Table 2 Dose Modification Guidelines for Lenvatinib-Everolimus Combination Treatment-Related Toxicity

Fourth occurrence (same toxicity or new toxicity)	Interrupt lenvatinib and everolimus	Discontinue study treatment
Grade 4^g: Discontinue Study Treatment		

For grading, see [Common Terminology Criteria for Adverse Events \(CTCAE v4.03. \(Appendix 3\)\)](#). Collect all CTC grades of AEs, decreasing and increasing grade.

- a: Interruption of study treatment for more than 28 days (due to treatment-related toxicities) will require Sponsor’s approval before treatment can be resumed.
- b: Initiate optimal medical management for nausea, vomiting, hypothyroidism, hypertension and/or diarrhea before any study treatment interruption or dose reduction. For treatment-related hypertension and non-infectious pneumonitis, refer to Management of Hypertension ([Section 9.4.2.2](#)) and Management of Non-infectious Pneumonitis ([Section 9.4.2.5](#)) for dose modification guidelines.
- c: Applicable only to those Grade 2 toxicities judged by the subject and/or physician to be intolerable.
- d: Obese subjects with weight loss do not need to return to the baseline weight or 10% of baseline weight (ie, Grade 1 weight loss). These subjects will restart the study drug(s) at a lower dose once their weight remains stable for at least 1 week and they reached the normal body mass index (BMI) (if the weight loss occurred but it is still above normal BMI, they can restart the study treatment at a lower dose once the weight has been stable for at least 1 week). Normal BMI should be used as the new baseline for further dose reductions.

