- e: For Grade 2 toxicity, resume everolimus at the same dose as prior to dose interruption. For Grade 3 toxicity, investigator will decide the probability of the event being related to one or both drugs as to whether dose modification of one or both drugs is required.
- f: For asymptomatic laboratory abnormalities, such as Grade ≥ 3 elevations of amylase and lipase that are not considered clinically relevant by the investigator, continuation of treatment should be discussed with the Sponsor.
- g: Excluding laboratory abnormalities judged to be non-life-threatening, in which case manage as Grade 3.

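### The design sentence that lenvatinib is reduced for Grade 3 or 4 TEAEs does not match the dose-modification section it cites, on Grade 4 events and on relatedness

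*Protocol*

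**What the plan says.** **Design text.** Protocol 9.1 reads: "If Grade 2 (intolerable) or Grade 3 or 4 TEAEs are observed, the lenvatinib dose will be reduced", and refers to the dose reduction section, which it names as Section 9.4.2. The synopsis (Study Design) reads: "If Grade 2 (intolerable) or Grade 3 or 4 TEAEs are observed, the lenvatinib dose will be reduced, as described below", pointing to its own dose reduction part. SAP 3.2 repeats the sentence but points to protocol Section 9.4.2.1.

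**Dose-modification text.** Section 9.4.2 defines its scope as: "Dose reduction and interruptions for subjects who experience lenvatinib-everolimus combination therapy-related toxicity", and sends hypertension and non-infectious pneumonitis to their own sections. For intolerable Grade 2 or Grade 3 toxicity, Table 2 interrupts treatment and lowers lenvatinib by one level on each of the first three occurrences. For Grade 4 toxicity its instruction is: "Discontinue study treatment". Footnote g gives one exception: "Excluding laboratory abnormalities judged to be non-life-threatening, in which case manage as Grade 3". The synopsis contains the same table, Grade 4 line and footnote.

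**Escalation text.** Under Section 9.4.1, a subject in the 14-mg arm with no intolerable Grade 2 or Grade 3-or-higher TEAE requiring a dose reduction in Cycle 1 moves up: "lenvatinib dose will be escalated to 18 mg QD". In 9.1, the sentence just before the design sentence carries the same condition.

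**The concern.** The dosing rule in the 14-mg arm is the experimental regimen, so the text that summarises it should agree with the text that governs it. Here a site that relies on the design section and a site that relies on Table 2 could act differently on the same event. The clearest case is a related, life-threatening Grade 4 event: one text lowers the lenvatinib dose and the other stops study treatment. That is a patient-safety matter whatever its statistical weight. The protocol also keeps subjects on study treatment after the data cutoff for the primary analysis, so the Grade 4 instruction still applies to anyone who remains on drug.

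**Working it through.** No arithmetic applies. The check sets the passages side by side, one type of event at a time.

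| Event | Design sentence (synopsis, 9.1, SAP 3.2) | Governing text | Agree? |
|---|---|---|---|
| Related Grade 3, first to third occurrence, covered by Table 2 | Reduce | Table 2: interrupt, then one level down | Yes |
| Related Grade 4 laboratory abnormality judged not life-threatening | Reduce | Footnote g: handled as Grade 3 | Yes, for the first three occurrences |
| Other related Grade 4 toxicity covered by Table 2 | Reduce | Table 2: stop study treatment | No |
| Unrelated Grade 3 or 4 TEAE | Reduce | Outside the scope of 9.4.2 and Table 2 | No |
| 14-mg arm, Cycle 1 Grade 3 TEAE that does not require reduction | Reduce, if read literally | 9.4.1 and the preceding sentence of 9.1: escalate to 18 mg | No, if read literally |

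1. **Grade 4.** The design sentence names Grade 4 and prescribes reduction. Table 2 prescribes discontinuation, and footnote g exempts one class of laboratory findings only. The synopsis holds both statements, so it disagrees with itself.

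2. **Relatedness.** Protocol 9.5.1.4.1 says an adverse event need not be causally related to the product. The TEAE definitions in protocol 9.7.1.8.2 and SAP 5.6.3 are not restricted to related events. The design sentence therefore includes unrelated events, which 9.4.2 does not cover.

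3. **Escalation condition (lesser point).** The escalation rule presupposes that some Grade 3 or higher TEAEs need no reduction. The protocol gives candidates:
   - unrelated events;
   - asymptomatic laboratory abnormalities under footnote f, where continuing treatment is to be discussed with the sponsor;
   - blood pressure of 160/100 mmHg or more, which SAP Table 8 places at Grade 3 and for which the numbered steps in 9.4.2.2 begin with continuing lenvatinib.

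   The design sentence drops the condition, so for such an event in Cycle 1 two adjacent sentences point in opposite directions if taken literally.

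4. **SAP reference.** SAP 3.2 cites 9.4.2.1. That section lists the dose steps, the limit of three reductions and the dispensing procedure. It contains neither the Grade 4 rule nor the relatedness limit, so the SAP reader is not sent to the text that would resolve the question.

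**The case against.** The best reply is that the design sentence is a summary that defers to 9.4.2, not a competing rule. A careful reader follows the reference, finds Table 2, handles an unrelated event as that section would, and carries the escalation condition over from the sentence before. Discontinuation for Grade 4 is also stated again for hypertension (9.4.2.2) and thromboembolic events (9.4.2.9). Up-titration is further referred to the IxRS and Pharmacy Manuals, which are not available here.

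Much of this stands. It makes the escalation point a literal reading of a summary, and it lowers the severity overall. It does not remove the conflict. The sentence names an action for Grade 4 and then cites a section that prescribes another. The SAP citation does not reach that section's rules, and no text says which statement prevails.

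A reader might also infer larger consequences, which the documents do not support:

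- **A distorted primary safety comparison.** The endpoint counts subjects with an intolerable Grade 2 or any Grade 3 or higher TEAE within 24 weeks, regardless of relatedness. A subject with a Grade 3 or 4 TEAE in that window already counts, whatever dose follows.
- **An ambiguous sensitivity analysis in SAP 5.4.1.** That section restates the escalation rule with the condition that the event requires dose reduction, so the group that should have been up-titrated is defined there and not by SAP 3.2. The analysis is also optional.
- **A dose gap of 18 − 10 = 8 mg, or 8/18 = 44%, for a Cycle 1 Grade 3 event.** This appears only if 9.4.2 is ignored on relatedness and Table 3, which sits inside 9.4.2, is then used to obtain 10 mg. Footnote f does not say that no reduction is needed.
- **A frequent problem, from the 36/51 (71%) with Grade 3 and 4 AEs in Study 205.** That is the combination arm starting at 18 mg, with no Cycle 1 restriction and no split by relatedness or between Grades 3 and 4. It does not measure how often the two texts diverge.

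**Conclusion.** The inconsistency is real and visible in the text. It is firm for Grade 4 events and for relatedness, and weaker for the escalation condition, which depends on a literal reading. The wrong section reference in SAP 3.2 is a separate small error.

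Its size cannot be quantified: the documents give no frequency for the events on which the texts differ. The sample size, non-inferiority margin and stopping boundaries do not depend on it, and no change in primary safety endpoint status or in the SAP 5.4.1 definition has been shown. The conclusion rests on the wording of the protocol and SAP alone. The manuals might settle practice at sites, but they would not make the two documents consistent. This is a should-fix clarification, justified by patient safety and not by any effect on the planned inference.

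**What to change.** Reconcile the sentence in the synopsis, protocol 9.1 and SAP 3.2 with Section 9.4.1, with Section 9.4.2 including Table 2 and its footnotes, and with the synopsis copy of that table. One consistent statement should settle three things:

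- what happens at Grade 4;
- whether the action depends on relatedness to treatment;
- how a Cycle 1 Grade 3 TEAE that does not require reduction bears on escalation.

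The sponsor has to decide the content; this review does not say which clinical rule is right. Correct the SAP 3.2 reference so that it leads to the full dose-modification rules.

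The cost is a protocol clarification and a matching SAP edit: one sentence in three places and one section number, plus any conforming change to the governing text. No new data are needed, and no planned analysis changes.

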9.1.1 Prerandomization

The Prerandomization Phase will last no longer than 28 days and will include a Screening Period to establish protocol eligibility and a Baseline Period to confirm eligibility and establish disease characteristics prior to randomization and treatment.

9.1.1.1 Screening Period

Screening will occur between Day -28 and Day -3. The purpose of the Screening Period is to obtain informed consent and to establish protocol eligibility according to the inclusion and exclusion criteria listed in [Sections 9.3.1](#) and [9.3.2](#), respectively. The screening assessment can serve as the baseline assessment if performed within 72 hours before randomization. Informed consent will be obtained after the study has been fully explained to each subject and before the conduct of any screening procedures or assessments. Procedures to be followed when obtaining informed consent are detailed in [Section 5.3](#).

Subjects must have a histological or cytological confirmed diagnosis of predominant clear cell RCC (original tissue diagnosis is acceptable) and documented evidence of advanced RCC.

The Screening Disposition case report form (CRF) page must be completed to indicate whether the subject is eligible to participate in the study and to provide reasons for screen failure, if applicable.

9.1.1.2 Baseline Period

The baseline assessment can be performed from Day -3 through Day -1 or prior to randomization on Cycle 1/Day1. The screening assessment can serve as the baseline assessment if performed within 72 hours before randomization. Laboratory tests and a pregnancy test (for female subjects of childbearing potential) may be performed up to 72 hours before randomization.

Subjects who complete the Baseline Period and meet the criteria for inclusion and exclusion ([Sections 9.3.1](#) and [9.3.2](#), respectively) will begin the Randomization/Treatment Phase.

9.1.2 Randomization Phase

The Randomization Phase will begin at the time of randomization of the first subject and will include both a Treatment Period and a Follow-Up Period. The data cut off for the primary analysis will occur at the end of the Randomization Phase, which is defined as when the last subject enrolled completes the Week-24 tumor or discontinues study treatment prior to Week 24. Subjects will be randomized in a 1:1 ratio. After the data cut off for the primary analysis, subjects who are still on study treatment will continue to receive investigational product until they complete the Off-Treatment Visit. The last subject last visit will be the date of the Off-Treatment Visit for the last subject's last assessment after the data cutoff for the primary analysis.

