The data cutoff for the primary analysis will occur at the end of the Randomization Phase, which is defined as the time the last subject enrolled completes the Week-24 tumor assessments or discontinues study treatment before Week 24. Subjects will continue to receive investigational product until they complete the Off-treatment visit. All subjects who are still on study treatment after the data cutoff for the primary analysis (ie, at the end of the Randomization Phase) will continue to receive investigational product until they complete the Off-Treatment Visit. The definition of the **End of Study** is the last subject's last assessment (Off-Treatment Visit) after the data cutoff for the primary analysis. At the End of Study, the Sponsor (or investigator where required) will ensure that all relevant IRBs/IECs and Competent Authorities are notified about the study completion per regulatory requirements in each country or region.

The sponsor should also provide the IRB/IEC with a summary of the study's outcome.

In the case of early termination/temporary halt of the study, the investigator should notify the IRB/IEC and CA within 15 calendar days, and a detailed written explanation of the reasons for the termination/halt should be given.

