Subjects will receive study treatment as continuous 28-day cycles. Treatment cycles will be counted continuously regardless of dose interruptions. Subjects will undergo safety and efficacy assessments as defined in the Schedule of Procedures/Assessments ([Table 6](#)) and in the Schedule of Assessments After the Data Cutoff for the Primary Analysis ([Table 7](#)). After the data cutoff for the primary analysis subjects will be eligible to receive study treatment as continuous 56-day cycles.

Subjects will discontinue study treatment upon evidence of progressive disease, as judged by the investigator. After disease progression, subjects will be followed for survival and PFS2 until the data cut-off for the primary analysis.

This study will consist of 2 phases, the Prerandomization Phase and the Randomization Phase with treatment continuing after the data cutoff for the primary analysis. An overview of the study design is presented in [Figure 8](#).

The data cutoff for the primary analysis will occur when all randomized subjects in the Randomization Phase have completed Week 24 assessments or have discontinued study treatment prior to Week 24. After the primary analysis is completed, subjects still receiving study treatment may continue taking lenvatinib and everolimus after the data cutoff for the primary analysis. Subjects will continue to receive investigational product after the data cutoff for the primary analysis until

they complete the Off-treatment visit. The definition of the **End of Study** is the last subject's last assessment (Off-Treatment Visit) after the data cutoff for the primary analysis.

The data obtained after the data cutoff for the primary analysis will be summarized and included in the CSR at the end of study as an addendum.

[figure not shown]

Figure 8 Study Design for Study E7080-G000-218

R = randomization

PD = progressive disease

PFS2 = PFS after next line of therapy

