9.7.1.1 Study Endpoints

9.7.1.1.1 PRIMARY ENDPOINTS

- Objective response rate at Week 24 (ORR_{24W}) as assessed by the investigator according to RECIST 1.1 ([Appendix 8](#)). ORR_{24W} is defined as the proportion of subjects with best overall response (BOR) of complete response (CR) or partial response (PR) at the Week-24 (after randomization) time point or earlier. To be considered a BOR, all responses must be confirmed no less than 4 weeks after the initial assessment of response.
- Proportion of subjects with intolerable Grade 2 or any \geq Grade 3 TEAEs within 24 weeks after randomization (as of the Week-24 time point).

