This study consists of 2 phases, the Pre-randomization Phase and the Randomization Phase, as shown in Figure 1:

[figure not shown]

Figure 1 Study Design for Study E7080-G000-218

R = randomization
 PD = progressive disease
 PFS2 = PFS on next line of therapy

- The Pre-randomization Phase will last no longer than 28 days and will include a Screening Period to establish protocol eligibility and a Baseline Period to confirm eligibility and establish disease characteristics prior to randomization and treatment.
- The Randomization Phase will consist of a Treatment Period and a Follow-up Period. It will begin at the time of randomization of the first subject and will end at the data cutoff for the primary analysis, which is defined as when all randomized subjects complete the Week-24 tumor assessments or discontinue study treatment before Week 24.

- The Treatment Period will begin with the first dose of study drug administration in Cycle 1 and continue in 28-day cycles until completion of the off-treatment assessments (within 28 days after the last study drug administration). Subjects will undergo safety and efficacy assessments as defined in the Schedule of Procedures/Assessments in protocol Table 6. Subjects will continue to receive study treatment until confirmed disease progression, development of unacceptable toxicity, subject request, withdrawal of consent, or study termination by the sponsor. Subjects who discontinue treatment before the data cut off for the primary analysis will enter the Follow-up Period, and will be followed every 12 weeks (± 1 week) after the off-treatment visit. If a clinic visit is not feasible, follow-up information may be obtained via telephone or email.

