- The Follow-up Period will begin immediately after the off-treatment assessments have been completed and will continue as long as the study subject is alive, until the study subject withdraws consent, or until the data cutoff for the primary analysis. Subjects who discontinue study treatment before disease progression will continue to undergo tumor assessments every 8 weeks and as of Amendment 06, send these to the imaging core laboratory (ICL) until documentation of disease progression or start of another anticancer therapy. Following the off-treatment visit, subjects will continue to be followed every 12 weeks (± 1 week) for survival and PFS2, and all anticancer treatments received will be recorded until the data cutoff for the primary analysis. This information will be recorded unless the information is not allowed to be provided due to confidentiality.

The data cutoff for the primary analysis will occur at the end of the Randomization Phase, which is defined as the time when all randomized subjects have completed Week 24 assessments or have discontinued study treatment prior to Week 24.

Subjects will continue to receive investigational product until they complete the off-treatment visit prior to their transition to commercial lenvatinib and everolimus or an access program. The last subject last visit for the End of Study will be the date of the off-treatment visit for the last subject.

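### Protocol 5.1 and 9.1.2 time the primary cutoff by the last subject enrolled, while the synopsis, Protocol 9.1 and SAP 3.2 require all randomized subjects; the two rules differ if that last subject stops treatment early

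*Protocol*

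**What the plan says.** The current text carries two definitions of the same cutoff.

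**One subject decides**
- Protocol 5.1: "the time the last subject enrolled completes the Week-24 tumor assessments or discontinues study treatment before Week 24".
- Protocol 9.1.2, which defines the Randomization Phase: "when the last subject enrolled completes the Week-24 tumor or discontinues study treatment prior to Week 24". The noun after 'tumor' is missing.

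**Every subject decides**
- Protocol 9.1: "when all randomized subjects in the Randomization Phase have completed Week 24 assessments or have discontinued study treatment prior to Week 24". The synopsis also uses an all-randomized rule.
- SAP 3.2, describing the Randomization Phase: "when all randomized subjects complete the Week-24 tumor assessments or discontinue study treatment before Week 24". It restates the rule for the cutoff itself: "the time when all randomized subjects have completed Week 24 assessments or have discontinued study treatment prior to Week 24".

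Both primary endpoints run over 24 weeks from randomization. Protocol 9.7.1.1.1 counts a best response of "complete response (CR) or partial response (PR) at the Week-24 (after randomization) time point or earlier", with confirmation at least 4 weeks later. For safety it counts intolerable Grade 2 or "Grade 3 TEAEs within 24 weeks after randomization (as of the Week-24 time point". Missing responses count as non-response (Protocol 9.7.1.6.4, SAP 5.3.5).

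**The concern.** A trigger that depends on one subject is met on the day that subject stops treatment, whatever the status of the others. Suppose the last enrollee stops at Week 8. Anyone randomized in the preceding 16 weeks and still on treatment then has less than 24 weeks of follow-up at the cutoff. Such a subject without a confirmed response becomes a non-responder, and one without a qualifying TEAE becomes event-free. Both proportions are biased downward, and both contrasts shrink.

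The lost safety information could not be fully recovered later. Protocol 9.5.1.4.1 and Table 7 limit adverse event recording after the cutoff to SAEs and events leading to drug discontinuation. A nonserious Grade 3 event, or an intolerable Grade 2 event handled by interruption or reduction, could then go unrecorded. Protocol 9.1.2.2 says that all AEs are captured, which conflicts with those sections and does not settle the matter.

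**Working it through.** **1. The plan's own figures.** Inputs from Protocol 9.7.2: response 37% (18 mg) and 45% (14 mg), margin OR 0.76, 1-sided alpha 0.05, 153 per arm.
- Planned OR = (0.45/0.55)/(0.37/0.63) = 1.393, so d = ln(1.393/0.76) = 0.606.
- v = 1/(0.37×0.63) + 1/(0.45×0.55) = 8.330.
- Fixed design: n per arm = v(1.645 + 0.842)²/d² = 140.3, or 281 in total.
- Simulating the group-sequential design at 150/200/306 with the stated boundaries (2 million runs) gives 80.1% power with futility applied, 82.3% without, and 1-sided alpha 0.0498. The stated 306 and 80% reproduce.
- Safety, 75% vs 60%, 2-sided 0.05, 153 per arm: 80.3% power, which also reproduces.

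**2. The two rules compared.** The all-randomized condition includes the last enrollee, so the one-subject cutoff can never fall later.
- Last enrollee reaches Week 24: everyone randomized before has reached it too, so the rules agree apart from scan windows.
- Last enrollee stops at week t < 24: the one-subject rule is met at t. The all-randomized rule waits for anyone still on treatment and short of Week 24.

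**3. How many could be exposed.** No accrual rate is given. *Assumption:* 338 subjects over 2 to 3 years, i.e. 338/104 = 3.25 or 338/156 = 2.17 per week. Upper limit = rate × (24 − t):

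| Last enrollee stops at | Others short of 24 weeks, at most | Share of 306 |
|---|---|---|
| Week 4 | 43–65 | 14–21% |
| Week 8 | 35–52 | 11–17% |
| Week 16 | 17–26 | 6–8% |

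Over a wider assumed range of 1.5 to 5 per week, the Week 8 figure runs from 24 to 80. The two interim DMC meetings in SAP section 6 were 13 weeks apart, for 150 and 200 subjects. That gives a rough proxy of 50/13 = 3.8 per week and a figure of 62. Meeting dates are only a weak guide to accrual.

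For a Week 8 stop, 2.17×4 to 3.25×4, or about 9 to 13 subjects, would have under 12 weeks of follow-up. With the first scheduled scan in Week 8 and confirmation at least 4 weeks later, almost none of them could be confirmed responders.

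**4. Effect on the tests: worst-case illustration.** Let 10% of each arm be truncated and all of them counted as having no event, so that every rate is multiplied by 0.9.
- Planned OR: (0.405/0.595)/(0.333/0.667) = 1.36, against 1.39.
- OR at the margin: 37% vs 30.9% becomes 33.3% vs 27.8%, and 0.76 moves to 0.77. This leans slightly toward a false non-inferiority claim.
- Efficacy power, single look at 0.045: Φ(d/√(v/153) − 1.695) falls from 82% to 78%.
- Safety power, 67.5% vs 54%: falls from 80% to 68%.

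**The case against.** The strongest reply is that the operative rule is already clear. The all-randomized wording stands in the synopsis, in Protocol 9.1 and twice in the SAP, and SAP section 4 ties the final inference to that cutoff. Of the two outliers, 5.1 is a section about ethics committees, and the sentence in 9.1.2 is visibly incomplete. Naming the last subject enrolled can be read as shorthand for the whole cohort reaching Week 24. A literal reading would also defeat endpoints fixed at 24 weeks. Most of this stands: the sponsor probably intends the all-randomized rule. It does not justify keeping two definitions, since 9.1.2 is the section that defines the phase.

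A reader might take the counts above as numbers of misclassified subjects. The documents do not support that. The counts include subjects already off treatment and those whose endpoint is settled by a confirmed response or a qualifying TEAE. The plan itself assumes that 75% and 60% have the safety event by Week 24. The power losses assume that no truncated subject has had an event, so they are a limit and not a forecast.

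Nor does follow-up simply stop. Subjects on treatment continue to be scanned at least every 12 weeks, and later data go into a CSR addendum. They fall outside the primary data, and adverse event capture is narrower.

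A separate gap exists under both rules. A subject counts as complete on the day treatment stops, although SAP 5.6.3 counts TEAEs up to 28 days after the last dose. This affects only subjects who stop before Week 24 and within 28 days before the cutoff. It is a minor refinement and not part of the contradiction.

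**Conclusion.** The contradiction is real and lies in current text. Harm needs three things together: the last enrollee stops early, others are then still on treatment short of Week 24, and 5.1/9.1.2 is followed over the SAP. A reader might infer that late enrollees will be truncated, or that the non-inferiority test is unsound. The documents support neither inference. No truncation occurs if the last enrollee reaches Week 24, and even the 10% worst case moves the planned odds ratio only from 1.39 to 1.36. The safety comparison is the more exposed of the two.

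The exposure of at most 35 to 52 subjects for a Week 8 stop rests on an assumed 2.2 to 3.3 subjects per week. The sample size and stated power are unaffected. The wording should be corrected because it governs when the primary database closes.

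**What to change.** In Protocol 5.1 and 9.1.2, replace the reference to the last subject enrolled with all randomized subjects, matching the synopsis, Protocol 9.1 and SAP 3.2. In 9.1.2, restore the word 'assessments' after 'Week-24 tumor'. With this rule the cutoff cannot fall before Week 24 for anyone still on treatment. The cost is an edit to two protocol sections. SAP 3.2 needs no change, and N stays at 306.

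Optional and minor: count an early stopper as complete at the earlier of Week 24 or 28 days after the last dose (or at death or withdrawal of consent), so that the TEAE window is closed. This has to be made wherever the cutoff is defined: the synopsis, Protocol 5.1, 9.1 and 9.1.2, and both statements in SAP 3.2. It delays the cutoff by at most 28 days relative to the all-randomized rule.
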